#### 17.3 Adverse Events

Adverse events (AEs) will be coded using the Medical Dictionary for Regulatory Activities (MedDRAd) and will be graded according to the National Center Institute Common Terminology Criteria for AEs (NCI NCI-CTCAE criteriae).

Adverse events will be analyzed in terms of their type, incidence, severity, and relationship to the trial treatment as determined by the Investigator.

Page 23 of 44

Of SOP SA-02.08 TPL Effective Date: 31 Mar 2016

TPL N°: eTPL SA-02-01

d MedDRA version current at the time of production of report

NCI CTCAE version 4.03 as per protocol

Related AEs are defined as events with a relationship to trial treatment equal to 'possibly related' or 'related' as determined by the Investigator according to protocol v3. For subjects enrolled under the protocol v5 or subsequent versions, the relationship to trial treatment is defined as 'Not related' or 'At least possibly related', and related AES are events with a relationship to trial treatment equal to 'At least possibly related'.

Version: 2.0

Summary tables for AEs described below will only include AEs that are treatmentemergent, i.e., AEs that started or worsened (taking into account the dates of grade changes) during the on-treatment period.

Adverse events collected during the pre-treatment period that do not worsen after treatment is initiated will be tabulated together with the medical history, by System Organ Class (SOC) and Preferred Term (PT), and will be included in the AE listings (marked with a flag). Adverse events collected during the follow-up period will be tabulated separately from the treatment-emergent AEs and will be included in the AE listings (marked with a flag).

See section 4.1 for definition of pre-treatment, on-treatment and post-treatment periods.

A summary table will present the number and percentage of subjects with at least one:

- Adverse event (AE)
- AE related to GEN1029
- Grade ≥3 AE
- Grade ≥3 AE related to GEN1029
- Serious AE
- Serious AE related to GEN1029
- AE leading to drug discontinuation
- AE leading to drug interruption
- AE leading to dose reduction
- SAE leading to drug discontinuation
- Medication errors or overdose
- Serious congenital anomaly/birth defect
- Serious medically significant
- Fatal AE
- Fatal AE related to GEN1029
- AE of special interestf: Elevation of Transaminasesg
- AE of special interest: Diarrhea

Page 24 of 44

In addition, time to onset of first AESI event (for subjects with at least one event), total number of AESI events, total number and percentage of AESI events with outcome of resolution, and time to resolution of each AESI event (for events which are resolved) will be summarized by AESI category using descriptive statistics. AESI events with partial start date will be imputed accordingly to the rules described in section 4.7. The same outputs will be created for the other event of interest: Pyrexia.

Time to onset of first AESI event will also be presented graphically by AESI category using Kaplan-Meier curves (one plot for each AESI category); in these Kaplan-Meier curves, subjects with no AESI will be censored at the end of the treatment period. Time to onset of first other event of interest: Pyrexia, using Kaplan-Meier curves will also be displayed.

AESI will also be presented graphically using swim lane plots. Plots will be performed individually for each subject, by dose level, and will show the reported AESI by category on a time-based x-axis (arrow will be used to show ongoing AEs). Plots will also include lines to show start date in the study (i.e., informed consent date) and last contact date of subject, as well as start and end dates of on-treatment period. Other event of interest: Pyrexia, will also be displayed on those swim lane plots.

Listings of all adverse events (including those from the pre and post-treatment periods) will be provided including the screening number/patient number (including site and country), age, race, sex, regimen, dose level, tumor type, verbatim, PT, SOC, duration of the event, highest severity, action taken, outcome, causality, date of onset, cycle of onset, date of resolution, days since the first dose, days since the latest dose, serious (Y/N), DLT (Y/N), infusion reaction (Y/N) and the treatment-emergent flag. AEs collected during the pre-treatment and post-treatment period will be flagged. Similar listings will also be created for each adverse events of interest separately.

Adverse Event will also be presented in a table by ADA status as applicable.

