For uric acid, grade 1 and grade 3 are defined with overlapping boundaries: >ULN - 10 mg/dl (590 µmol/L); for grade 1 without physiologic consequences and for grade 3 with physiologic consequences (no grade 2). In all listings, tables (e.g., shift-tables based on NCI-CTCAE-grade), and graphs (if applicable) where uric acid is presented with NCI-CTCAE grade: a footnote will be added:

"A uric acid value >ULN-590  $\mu$ mol/L is either NCI-CTCAE grade 1 if there is no physiological consequence or grade 3 if there is. In the absence of physiological consequence information and for the purpose of presentation in this listing/table/graph, such values are here considered to be grade 1".

All summaries described below will be generated separately for hematology, coagulation, and biochemistry tests. Each dose level will have its own color and pattern. Individual subject's data over time per parameter and dose level will be plotted in individual profiles plots for the liver parameters. Abbreviated subject numbers are put at the beginning of the profile. Liver parameters will be presented in individual plots: ALT, AST, ALP, Total bilirubin and GGT will be plotted, with normalized values. Those five parameters will be presented in panel plots simultaneously and by dose level.

For laboratory tests where grades are defined by the NCI-CTCAE V4.3, the number and percentage of subjects by highest post-baseline (on-treatment) NCI-CTCAE grade will be presented, regardless of baseline.

Shift tables will be produced for all laboratory parameters graded by NCI-CTCAE grading to compare baseline grade to the highest on-treatment grade per subject. These tables will summarize the number of subjects with each baseline NCI-CTCAE grade and changes to the maximum NCI-CTCAE grade. For the calculation of the maximum NCI-CTCAE grade, both scheduled and unscheduled values available post baseline will be used.

Shift tables in Low/Normal/High categories will be displayed when NCI-CTCAE grading is missing. These tables will summarize the number of subjects going from Normal/Low at

Page 27 of 44

TPL N°: eTPL SA-02-01 Of SOP SA-02.08 TPL Effective Date: 31 Mar 2016

baseline to High at any post-baseline and going from Normal/High at baseline to Low at any post-baseline. Both scheduled and unscheduled values available during the treatment period will be used.

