Table 14.03.16.03	Treatment Emergent Adverse Events of Special Interest: Elevation of Transaminases - by SOC and Preferred Term	Safety Set

Table 14.03.16.04	Treatment Emergent Adverse Events of Special Interest: Elevation of Transaminases - by SOC	Safety Set
	and Preferred Term and CTCAE Grade	
Table 14.03.16.05	Treatment Emergent Adverse Events of Special Interest: Elevation of Transaminases - by Preferred Term, CTCAE Grade and by Cycle	Safety Set
Table 14.03.16.06	Time to Onset of First Treatment Emergent Adverse Event of Special Interest: Elevation of Transaminases , with Outcome of Resolution and Time to Resolution	Safety Set
Table 14.03.17.01	Treatment Emergent Adverse Events of Special Interest: Diarrhea - by Preferred Term	Safety Set
Table 14.03.17.02	Treatment Emergent Adverse Events of Special Interest: Diarrhea - by Preferred Term and Cycle	Safety Set
Table 14.03.17.03	Treatment Emergent Adverse Events of Special Interest: Diarrhea - by SOC and Preferred Term	Safety Set
Table 14.03.17.04	Treatment Emergent Adverse Events of Special Interest: Diarrhea - by SOC and Preferred Term and CTCAE Grade	Safety Set
Table 14.03.17.05	Treatment Emergent Adverse Events of Special Interest: Diarrhea - by Preferred Term, CTCAE Grade and by Cycle	Safety Set
Table 14.03.17.06	Time to Onset of First Treatment Emergent Adverse Event of Special Interest: Diarrhea, with Outcome of Resolution and Time to Resolution	Safety Set
Table 14.03.18.01	Other Treatment Emergent Adverse Events of Interest: Pyrexia - by Preferred Term	Safety Set
Table 14.03.18.02	Other Treatment Emergent Adverse Events of Interest: Pyrexia - by Preferred Term and Cycle	Safety Set
Table 14.03.18.03	Other Treatment Emergent Adverse Events of Interest: Pyrexia - by SOC and Preferred Term	Safety Set
Table 14.03.18.04	Other Treatment Emergent Adverse Events of Interest: Pyrexia - by SOC and Preferred Term and CTCAE Grade	Safety Set
Table 14.03.18.05	Other Treatment Emergent Adverse Events of Interest:	Safety Set

	Pyrexia - by Preferred	
	Term, CTCAE Grade and	
T. I	by Cycle	
Table 14.03.18.06	Time to Onset of First Other Treatment Emergent	Safety Set
	Adverse Events of Interest:	
	Pyrexia , with Outcome of	
	Resolution and Time to	
	Resolution	
Table 14.03.19	Related Treatment	Safety Set
	Emergent Adverse Events	
	of Special Interest: Elevation of Transaminases	
	- by Preferred Term	
Table 14.03.20	Related Treatment	Safety Set
	Emergent Adverse Events	,
	of Special Interest:	

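### Time to resolution of AESIs and pyrexia is summarised only among resolved events, so it leans towards faster resolution by an amount set by the share of events left open

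*SAP*

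**What the plan says.** For each AESI category (transaminase elevation and diarrhea), SAP 17.3 states: "time to resolution of each AESI event (for events which are resolved) will be summarized by AESI category using descriptive statistics". For fever: "The same outputs will be created for the other event of interest: Pyrexia". The outputs are Tables 14.03.16.06, 14.03.17.06 and 14.03.18.06, each titled time to onset of the first event, "with Outcome of Resolution and Time to Resolution".

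The plan also keeps unresolved events in view:

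- The same sentence of SAP 17.3 asks for the "total number and percentage of AESI events with outcome of resolution".
- Swim lane plots are drawn for each subject, in which an "arrow will be used to show ongoing AEs".
- All AEs are listed with duration, outcome and resolution date, and "Similar listings will also be created for each adverse events of interest separately".
- In SAP 17.5, "Individual subject's data over time per parameter and dose level will be plotted in individual profiles plots for the liver parameters".

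For time to onset, the plan adds Kaplan-Meier curves to the descriptive summary, and "in these Kaplan-Meier curves, subjects with no AESI will be censored at the end of the treatment period". The text of SAP 17.3 describes no censored or cumulative-incidence summary of time to resolution.

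**The concern.** A duration summarised only over events that have ended is conditional on having ended within follow-up. Events that outlast follow-up are left out rather than censored, and they are the slower ones on average. The resulting mean and median can only lean short.

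Open events are plausible here. Protocol 10.2.13 has an outcome for events that have not resolved, and 10.2.14 requires no end date for them. In the dose escalation part, the only part analysed, Protocol 8.2 withdraws a patient from the trial, safety follow-up included, when another anti-cancer treatment starts. Death and loss to follow-up also close the record.

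The unit of analysis adds a second problem. Each event counts once, so a subject with several short episodes outweighs a subject with one long one. The transaminase category pools the preferred terms for raised AST, raised ALT and raised transaminases, so one hepatic episode coded under two terms can enter twice.

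The quantity is of interest. Protocol 6.4.1 reports transaminase elevation of grade 2 or higher in 14 of 27 patients, and Protocol 10.3.2 reports diarrhea in more than 40%. A reader will want to know how quickly these events reverse.

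**Working it through.** The documents give no figure for time to resolution, so there is none to reproduce. They also give neither the unresolved share nor the distribution of resolution times. Everything below therefore rests on assumed resolution and follow-up times, shown over a range.

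**1. Fixed follow-up, exponential resolution.** Let m be the true median in days, λ = ln 2 / m, and C the days of follow-up after onset. The share resolved is p = 1 − exp(−λC). The resolved-only median is −ln(1 − 0.5p)/λ. For m = 14 and C = 28, p = 0.75 and the median is −ln(0.625)/0.0495 = 9.5 days.

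| True median | C | Resolved | Resolved-only median | Ratio to truth |
|---|---|---|---|---|
| 7 | 70 | about 100% | 7.0 | 1.00 |
| 14 | 70 | 97% | 13.4 | 0.96 |
| 28 | 70 | 82% | 21.4 | 0.77 |
| 56 | 70 | 58% | 27.6 | 0.49 |
| 7 | 28 | 94% | 6.4 | 0.91 |
| 14 | 28 | 75% | 9.5 | 0.68 |
| 28 | 28 | 50% | 11.6 | 0.42 |

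The 70-day rows reflect the safety follow-up visit 70 days after last dose. The 28-day rows stand for early loss.

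**2. Random follow-up.** With independent exponential resolution (median m) and follow-up (median c), the unresolved share is m/(m + c) and the resolved-only median is mc/(m + c). For m = 14 and c = 30: 14/44 = 32% unresolved, and 420/44 = 9.5 days. For m = 7 and c from 21 to 60: 147/28 = 5.3 to 420/67 = 6.3 days.

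**3. Some events never resolve.** Let a fraction u never resolve, with exponential times for the rest. The time by which half of all events have resolved, divided by the resolved-only median, is −ln((0.5 − u)/(1 − u))/ln 2.

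| u | 5% | 10% | 20% | 30% | 40% |
|---|---|---|---|---|---|
| Ratio | 1.08 | 1.17 | 1.42 | 1.81 | 2.58 |

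For u = 20%: −ln(0.3/0.8)/ln 2 = 0.981/0.693 = 1.42.

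**4. Does keeping the open events repair it?** A simulation used 5,000 runs of 25 events (48 × 14/27 = 24.9), lognormal resolution times with log SD 1, and uniform censoring independent of resolution, without deaths.

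| True median | Mean censoring time | Resolved | Resolved-only | Kaplan-Meier |
|---|---|---|---|---|
| 14 | 28 | 65% | 10.1 | 13.9 |
| 14 | 70 | 84% | 12.5 | 14.2 |
| 28 | 28 | 44% | 15.4 | 27.4 |
| 28 | 70 | 71% | 21.7 | 28.3 |

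The resolved-only column is the mean over runs and the Kaplan-Meier column the median over runs. Retaining open events as censored brings the median back to about the true value.

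**The case against.** The plan does not conceal unresolved events. The restriction is stated in the sentence itself, the percentage resolved sits in the same table, and the swim lane plots, listings and liver profiles show what is still open. A long event that resolves stays in, and SAP 4 requires quartiles, minimum and maximum, so that tail is shown. All of this stands. What it does not do is correct the median: a percentage printed beside a conditional median leaves the reader to combine the two.

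Planned follow-up is also longer than the gloomier settings above imply. Protocol 10.2 and 10.6 follow AEs at least to the safety follow-up visit unless they resolve first, and carry SAEs and possibly related grade 3 or higher events beyond end of trial. Protocol 6.4.1 describes transaminase elevation as mainly a first-dose effect, so many events start early. A 30-day exponential follow-up median would mean 1 − 2^(−7/30) = 15% of events lost within a week, and 1 − 2^(−70/30) = 80% with under 70 days. That is pessimistic, so the one-third shortfall it produces is an illustration and not an estimate for this trial.

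The contrast with time to onset is weaker than it looks, because the descriptive summary of onset is also restricted to subjects with an event and Kaplan-Meier is an added graph. Finally, 48 subjects over six biweekly dose levels will not support a stable curve for each dose, and the SAP itself warns that few events limit Kaplan-Meier. That argues for a pooled estimate, not for leaving it out.

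**Conclusion.** The time-to-resolution summary is conditional on resolution and per event, and it leans towards faster resolution whenever events remain open. The direction is certain; the size is not. It is near nil if almost all events resolve in follow-up (0 to 4% on the median for a true median of 7 to 14 days with a full 70 days). It becomes material when about 20% or more stay open, about 1.4-fold if 20% never resolve. These sizes assume exponential times and, in the random-follow-up and simulated settings, follow-up unrelated to resolution. If withdrawal is related to slow resolution, censoring reduces the bias without removing it.

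A reader might infer three stronger things that the documents do not support:

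- That unresolved or long events vanish from the report. They do not; only open events leave this one statistic.
- That reversibility will be reported as faster by some known amount. No unresolved share is given.
- That DLT counts, the MTD or restart decisions are affected. Those rules judge return to grade 1 or lower within 7 days, patient by patient, and do not draw on these tables.

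This is a modest weakness in a descriptive safety output, worth correcting because correction is cheap.

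**What to change.** In SAP 17.3 and the three tables:

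1. Keep the planned statistic and the percentage resolved, and label the former 'among resolved events'.
2. Add a cumulative-incidence (Aalen-Johansen) summary of time to AE resolution over all events. Censor open events at the last AE assessment and treat death as a competing event. Plain Kaplan-Meier with censoring at death would overstate resolution, because it treats patients who died unresolved as still able to resolve.
3. Use the first episode per subject as the headline and all events as support. Say how concurrent ALT and AST records are combined into an episode.
4. Pool over dose levels. Give the estimated proportion resolved at stated days, described as resolution by AE outcome and end date, not as the protocol's return-to-grade-1 criterion. If fewer than half resolve, report the median as not reached.
5. State whether resolution with sequelae counts as resolution. Derive resolution from the outcome field, since Protocol 10.2.14 also requires an end date for fatal events.
6. Reconcile Protocol 10.2 (follow AEs to end of trial) with 10.6 (follow to the safety follow-up visit), because this sets where open events are censored.

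The cost is SAP wording and a small programming change to three tables, with no new data. The downside is imprecision, which would be severe if the estimates were split by dose level.

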#### 17.4 Deaths and Serious Adverse Events

In addition to the tables presented in section 17.3, Fatal AEs, SAEs and NCI-CTCAE grade ≥ 3 AEs will be presented also by ADA positivity and by preferred term.

The number of deaths will be tabulated by source and total. The primary cause of death will be included in the listing. Number of deaths within 30 days of first dose of IMP, within 100 days of first IMP, and after 100 days after first IMP will also be tabulated.

## 17.5 Clinical Laboratory Data

The following laboratory parameters are measured:

 Biochemistry parameters: Sodium, potassium, magnesium, creatinine, calcium, blood urea nitrogen, AST, ALT, alkaline phosphatase, albumin, glucose, total bilirubin, direct bilirubin, lactate dehydrogenase, uric acid, Creactive protein, lipase, amylase, gamma-glutamyl transferase, glycosylated hemoglobin, chloride, cholesterol, triglycerides, high-density lipoprotein and low-density lipoprotein (calculated).

Page 26 of 44

TPL N°: eTPL SA-02-01 Of SOP SA-02.08 TPL Effective Date: 31 Mar 2016

- Hematology parameters: red blood cell count, hemoglobin, hematocrit, mean corpuscular volume, mean corpuscular hemoglobin, mean corpuscular hemoglobin concentration, white blood cell count with differential, platelet count, reticulocyte count and coagulation factors (prothrombin time, international normalized ratio and activated partial thromboplastin time).
- Urinalysis parameters: pH, density, protein, glucose, blood, leukocytes, bilirubin, and Beta-HCG

Safety laboratory assessments (biochemistry, hematology and urinalysis) will be graded using NCI-CTCAE v4.03 if possible. Grading will be assigned programmatically. The calculations of NCI-CTCAE grades will be based on the observed laboratory values. For local laboratory assessments, if a grade higher than 0 is attributed when the value is within normal range, then the grade will be put equal to 0. NCI-CTCAE grade 0 will be assigned for all non-missing values not graded as 1 or higher. For laboratory tests where grades are not defined by the NCI-CTCAE, results will be categorized as low/normal/high based on laboratory normal ranges. All laboratory assessments will be converted to the corresponding international system of unit. Values >xx or <xx will be imputed with respectively 1 value lower or 1 value higher according precision. For example, <50 will be imputed by 49, >35.6 will be imputed by 35.7. Only central labs will be used in summary tables. Local and central laboratory assessments will be used for the subject profile plots. Normalized values can be presented with different symbols.

For uric acid, grade 1 and grade 3 are defined with overlapping boundaries: >ULN - 10 mg/dl (590 µmol/L); for grade 1 without physiologic consequences and for grade 3 with physiologic consequences (no grade 2). In all listings, tables (e.g., shift-tables based on NCI-CTCAE-grade), and graphs (if applicable) where uric acid is presented with NCI-CTCAE grade: a footnote will be added:

"A uric acid value >ULN-590  $\mu$ mol/L is either NCI-CTCAE grade 1 if there is no physiological consequence or grade 3 if there is. In the absence of physiological consequence information and for the purpose of presentation in this listing/table/graph, such values are here considered to be grade 1".

All summaries described below will be generated separately for hematology, coagulation, and biochemistry tests. Each dose level will have its own color and pattern. Individual subject's data over time per parameter and dose level will be plotted in individual profiles plots for the liver parameters. Abbreviated subject numbers are put at the beginning of the profile. Liver parameters will be presented in individual plots: ALT, AST, ALP, Total bilirubin and GGT will be plotted, with normalized values. Those five parameters will be presented in panel plots simultaneously and by dose level.

For laboratory tests where grades are defined by the NCI-CTCAE V4.3, the number and percentage of subjects by highest post-baseline (on-treatment) NCI-CTCAE grade will be presented, regardless of baseline.

Shift tables will be produced for all laboratory parameters graded by NCI-CTCAE grading to compare baseline grade to the highest on-treatment grade per subject. These tables will summarize the number of subjects with each baseline NCI-CTCAE grade and changes to the maximum NCI-CTCAE grade. For the calculation of the maximum NCI-CTCAE grade, both scheduled and unscheduled values available post baseline will be used.

Shift tables in Low/Normal/High categories will be displayed when NCI-CTCAE grading is missing. These tables will summarize the number of subjects going from Normal/Low at

Page 27 of 44

TPL N°: eTPL SA-02-01 Of SOP SA-02.08 TPL Effective Date: 31 Mar 2016

baseline to High at any post-baseline and going from Normal/High at baseline to Low at any post-baseline. Both scheduled and unscheduled values available during the treatment period will be used.

# 17.6 Vital Signs, Physical Findings and Other Observations Related to Safety

Abnormal physical examination results will be tabulated and listed over time by body system.

Descriptive statistics (actual values and changes from baseline) over time will be given for body weight as it is important for the dosing.

Vital signs results will be listed by subject with a flag marking the clinically notable values for each of the following parameters:

Clinically notable elevated values

- Systolic BP: >=180 mmHg and an increase >=20 mmHg from baseline
- Diastolic BP: >=105 mmHg and an increase >=15 mmHg from baseline
- Weight: Increase from baseline of >=10%
- Heart rate: >=120 bpm with increase from baseline of >=15 bpm
- Temperature: >38 °C

Clinically notable below normal values

Page 28 of 44

Of SOP SA-02.08 TPL Effective Date: 31 Mar 2016

TPL N°: eTPL SA-02-01

- Systolic BP: <=90 mmHg and a decrease >=20 mmHg from baseline
- Diastolic BP: <=50 mmHg and a decrease >=15 mmHg from baseline
- Weight: decrease from baseline of >=10%
- Heart rate: <=50 bpm with decrease from baseline of >=15 bpm
- Temperature: <35 °C

The number of subjects with at least one clinically notable value as defined above will be summarized in a table.

